Patients enrolled in the trial will be randomized to treatment with or without electrical stimulation via an auricular, transcutaneous vagus nerve stimulator. All patients will be fitted with the device, we will attach adhesive contacts to the left ear. Stimulation sessions will occur for 20 minutes twice daily during the inpatient period. Patients assigned to the controls arm will have no electricity applied,

those treated with stimulation will be treated with the following parameters: frequency 20 Hz, pulse width 250 μ m, and varying intensities from 0.4 mA to 2 mA (intensity is always titrated to be a level below painful threshold in a patient). The amplitude of stimulation may be reduced if a patient complains of discomfort at the site of stimulation. The site of stimulation will be inspected daily before and after treatment to ensure there is no redness or irritation at the site.

Outcome Measure(s)

The primary endpoints of the study will be changes in the levels of inflammatory markers that include IL-1b, IL-6, TNF-α, and white blood cell count in the blood, as well as specific inflammatory cell counts (neutrophil to lymphocyte ratio, for example) at time of admission, and every day throughout the hospitalization. The secondary exploratory endpoints will be clinical outcomes assessed via the change in daily NIHSS and mRS at 30 and 90 days, as well as safety endpoints with regards to blood pressure and heart rate. We will also do mononuclear cell genetic testing to attempt to identify phenotypes that respond to the intervention. Follow up data will be obtained via chart review, we will obtain the mRS data at 30 days over the phone, and we will make additional outpatient follow up appointments for the research study in order to collect the NIHSS and mRS data at 90 days.

Analytical Plan

Results will be analyzed initially using descriptive statistics. Comparison between groups will be done using chi square tests for proportions, and t-tests or ANOVA procedures for continuous variables. Regression analysis will be performed to identify independent outcome predictors. Other inferential statistical analysis will be conducted as appropriate. Please see document with statistical plan that is attached.

Human Subjects Protection

Subject Recruitment Methods

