Statistical analyses were performed using Stata/MP version 18 (StataCorp LLC 2023, Statistical Software, College Station, TX) and Python packages Scipy and Statsmodels. All continuous variables were retained as continuous, except where noted. Multivariable regression was used to examine treatment group associations with outcomes, except for rare secondary outcomes/adverse effects. Following FDA recommendations, an intention-to-treat (ITT) approach was implemented. Primary ITT analyses were conducted without transformation of continuous outcome variables because ≥35 observations were available.

Statistical analysis of rate of change in cytokines, WBC, and neurological outcomes in taVNS vs. sham treatment.

Longitudinal data were analyzed using mixed effects models per the FDA, with person as a random effect, given multiple records per person. For cytokine models, assay plate was included as an additional random effect. This approach accommodated irregularly timed points, less restrictive missing data assumptions, and time-varying variables. To complement our primary ITT approach, treatment also was handled as time-varying when noted, with assignment occurring at randomization. All longitudinal models included treatment, time since LKN, and their interaction term(s) as primary independent variables to test whether the pattern of change over time differed between the taVNS and sham groups. Time was modeled quadratically for cytokine and WBC outcomes to capture the known U-shaped associations with time when modeling these outcomes and linearly for in-hospital NIHSS scores based on panel data plots. For NIHSS, a single model was constructed to estimate the rate of change (change in NIHSS per

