day) in each of the two treatment groups and to formally test whether these rates were different. For 30-day NIHSS changes (vs. baseline) and 90-day mRS changes, we used the parallel model, with actual assessment days scaled to standardize the evaluation period to 30 or 90 days, respectively. We characterized the daily change in each WBC or cytokine outcome using a similar model expanded to include the quadratic terms. Treatment-time interactions were tested using likelihood ratio tests comparing models with and without interaction term (NIHSS, mRS) or terms (cytokines, WBC), with significance at two-sided α =0.05. These analyses were adjusted for baseline covariates, including baseline NIHSS (except in NIHSS models, which included this observation), time from LKN to thrombus removal time or recanalization attempt (groin puncture time), and percent reperfusion (0-100%) based on TICI score to obtain a single semicontinuous measure. In sensitivity analyses, we also performed the analysis with a dichotomized TICI scale (reperfused ≥2B, not reperfused <2B) or restricted data to the first five days post-LKN (when most stimulations and hospitalizations had ended). Finally, we explored whether any difference in longitudinal patterns between taVNS and sham depended any of the a priori adjustment variables, i.e., whether any time-treatment interaction depended on one of these three variables. We conducted post-hoc t-tests to compare cytokine levels between groups on each day.

Statistical analysis of safety and exploratory analysis of the Stroke Complications and Poor Outcomes in relation to treatment.

To assess our dichotomous safety endpoints, we used logistic regression models constructed to assess differences in bradycardia, hypotension, infection, hemicraniectomy, hemorrhagic transformation, and deaths amongst treated vs non-treated patients. To explore the hypothesis that taVNS reduces the incidence of complications and poor outcomes, we performed logistic

regression models for discharge related outcomes, defined as: readmission, length of stay, and hospital poor disposition (i.e. nursing home, long-term acute care hospital, or death).

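### The daily cytokine, WBC and NIHSS models name person but no random slope, so their treatment-by-time tests exceed 5% type I error if patients' rates of change differ

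*Combined protocol and SAP*

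**What the plan says.** All of this is in the Expanded Statistical Analysis, in the part on rate of change, unless noted.

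- Random effects: "Longitudinal data were analyzed using mixed effects models per the FDA, with person as a random effect, given multiple records per person". Then: "For cytokine models, assay plate was included as an additional random effect". Nothing else is said about covariance.
- Fixed effects: "All longitudinal models included treatment, time since LKN, and their interaction term(s) as primary independent variables". "Time was modeled quadratically for cytokine and WBC outcomes"; in-hospital NIHSS is linear in time.
- Scale: "Primary ITT analyses were conducted without transformation of continuous outcome variables".
- Test: "Treatment-time interactions were tested using likelihood ratio tests comparing models with and without interaction term" (one term for NIHSS and mRS, more than one for cytokines and WBC), at two-sided 0.05.
- Sensitivity analyses: one recodes TICI; the other keeps only the first five days after last known normal, by which time, the text says, most stays were over. Neither changes the covariance structure.
- Protocol, Outcome Measure(s): "The primary endpoints of the study will be changes in the levels of inflammatory markers", measured at admission and daily in hospital.

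**The concern.** The text does not use the word intercept. But the reason it gives for the person effect is repeated records, and plate is handled in the same way. Both point to a random intercept for each.

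Under that model, all patients in an arm share one trajectory apart from a vertical shift. If some patients' markers or NIHSS scores move faster than others', the model spreads part of that between-patient variation over the daily residuals and treats it as independent noise. The information about a difference in slopes comes from about 80 patients, but the model credits it with something closer to the number of daily records. A plate effect does not represent a patient's slope.

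The plan does not itself treat a common rate as settled: it explores whether the time-treatment pattern depends on baseline NIHSS, time to recanalization or reperfusion. The main models are only adjusted for these variables; no covariate-by-time term is stated.

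At stake is the primary comparison. A device with no effect could be declared to alter marker trajectories more often than 1 time in 20, and intervals for rate of change would be too narrow for planning a later trial.

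**Working it through.** **Inputs from the documents:** about 80 patients (Sample size), daily records, linear or quadratic time, likelihood ratio test at 0.05.

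**Assumptions:** 40 per arm (no allocation ratio is stated), number of records per patient, residual SD and person-slope SD. The documents give none of these.

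**The plan's own figure.** With no slope variation the closed form below gives 0.050. Simulated random-intercept likelihood ratio tests (1,500 runs per setting) gave 0.045 to 0.061, which is nominal within simulation error.

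**Closed form, linear model, T equally spaced daily records.** Let s be the residual SD, sb the slope SD and Sxx the sum of squared deviations of time.

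- True variance of a patient's fitted slope is proportional to s² + sb²·Sxx.
- The random-intercept model uses s² + sb²·Sxx/(T−1).
- Ratio = (s² + sb²·Sxx) / (s² + sb²·Sxx/(T−1)); type I error = 2·(1 − Φ(1.96/√ratio)).

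Example with NIHSS, s = 1.5, sb = 0.5 points per day, T = 5, Sxx = 10: ratio = (2.25 + 2.5)/(2.25 + 0.625) = 1.65; 1.96/√1.65 = 1.52; type I error = 0.127.

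| Records per patient | sb = 0.25 | sb = 0.5 | sb = 1.0 |
|---|---|---|---|
| 2 | 0.050 | 0.050 | 0.050 |
| 3 | 0.053 | 0.062 | 0.087 |
| 4 | 0.060 | 0.087 | 0.150 |
| 5 | 0.073 | 0.127 | 0.222 |
| 6 | 0.092 | 0.178 | 0.290 |

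Simulated likelihood ratio tests at five records gave 0.062/0.114/0.208, in line with the formula. Unequal stays make it worse:

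- 2-7 records, 80% of patients at five or fewer: 0.098/0.201/0.328.
- 2-10 records, 65% at five or fewer: 0.162/0.312/0.448 (0.049 with no slope variation).
- The same 2-10 stays cut at five records, as in the sensitivity analysis: 0.072/0.116/0.220.

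**Quadratic 2-df test, the form used for the primary markers.** Slope SD is in residual SDs per day, so no outcome scale is assumed.

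| Setting | 0.1 | 0.2 | 0.3 | 0.5 |
|---|---|---|---|---|
| 5 records (1,500 runs) | 0.057 | 0.071 | 0.115 | 0.144 |
| 7 records (1,500 runs) | 0.065 | 0.131 | 0.177 | 0.258 |

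Further runs at slope SD 0.2/0.4 gave 6%/9-10% with five records, 9%/15% with six, and 18-21%/38-40% with 2-10. With 2-7 records (80% at five or fewer, 600 runs), slope SD 0.2/0.33/0.5 gave 0.112/0.170/0.282.

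**With assay plate simulated and fitted** (80 patients, five records, plate SD 0.5 residual SD, 500 runs), at slope SD 0/0.2/0.4: 0.056/0.074/0.106 if a patient's samples share a plate; 0.048/0.048/0.096 if they are scattered.

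**Does a random slope repair it?**

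- Linear, 2-10 records: 0.060/0.055/0.055 at sb = 0.25/0.5/1.0 (400 runs).
- Quadratic, six records, slope SD 0.2/0.4: 0.062/0.058, against 0.086/0.148 for intercept only (500 runs).
- With curvature also varying (SD 0.2 residual SD per day², slope SD 0.4, 600 runs): intercept only 0.245, random slope 0.140, random slope plus random quadratic 0.055.

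**Models not affected.** The 30-day NIHSS and 90-day mRS change models, read as two records per person at common scaled times, give a ratio of exactly 1 at T = 2. Simulation gave 0.060, 0.058 and 0.047 at slope SD 0, 1 and 2.

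**The case against.** The strongest reply is that the documents establish only an under-specified covariance. The inflated test needs two further conditions: that the model is intercept-only and that slopes vary. Both are conditions of this point. Even on the mildest reading, the primary model's random effects are not fully stated.

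Second, the size depends on assumptions. With five equal records and a slope SD of 0.1 residual SD, error is close to nominal (5.2% linear, 5.7% quadratic). With three or four records the NIHSS figures run only from 5% to 15%. At the other end, an NIHSS slope SD of 1.0 point per day over ten daily records implies an SD of 9 points in true change between patients; nothing in the documents supports that, and the 45% figure should carry little weight. This stands. The five-record and 2-7-record quadratic results are the fairer guide, because they concern the primary endpoint and fit the remark that most stays ended by day five.

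Third, there are partial safeguards. The five-day analysis reduces the inflation but does not remove it. The daily t-tests on cytokines do not rely on the longitudinal covariance, but they are post hoc and do not test a difference in trajectory.

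Fourth, the random-slope remedy was not simulated together with plate and quadratic time, and the fallback below was not simulated with plate. That also stands.

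Finally, this is a pilot. It nevertheless sets a 0.05 threshold and estimates rates of change, and its error rate and intervals should be as stated.

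**Conclusion.** The concern holds, conditionally. As described, the daily cytokine, WBC and NIHSS models read as random-intercept models, and their treatment-by-time tests are anti-conservative if patients differ in rate of change. For the primary markers with five daily records, error runs from near 5% at small slope variation to about 10% at a slope SD of 0.4 residual SD and 14% at 0.5. Unequal stays raise it, to 11-28% for 2-7 records at slope SD 0.2 to 0.5. These figures rest on 40 per arm and on assumed variances and stay lengths. With no slope variation the planned test is correct, and the two-record 30-day and 90-day models are outside the point. It should be fixed; confidence is medium because the documents give neither the fitted structure in full nor any slope variance.

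**What to change.** For the daily cytokine, WBC and NIHSS models, state a person random intercept and random slope for time with unstructured covariance. For cytokines and WBC, add a random quadratic term where it can be estimated. Keep assay plate for cytokines. Run the interaction likelihood ratio test by maximum likelihood on that model. If a random slope was already fitted, say so.

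State a fallback in advance: if the model does not converge or curvature cannot be modelled, replace the likelihood ratio test with a Wald F test on person-clustered standard errors with a small-sample correction (Mancl-DeRouen or person jackknife). The correction matters. With 2-10 records, the uncorrected clustered Wald test gave 0.068-0.079 (linear) and 0.110-0.146 (quadratic); the Mancl-DeRouen F test gave 0.050 and 0.065-0.074. For cytokines, report how samples were allocated to plates, since clustering on person does not account for patients who share a plate.

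The cost is about two sentences of text and one or two random-effect terms. The section is written in the past tense, so models already fitted would need refitting. No new data are needed. The price is wider intervals and lower power if slopes vary, some convergence failures, and a fallback that is only approximate when stays are very unequal.

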Cover page

Title: Neuromodulation Using Vagus Nerve Stimulation Following Ischemic Stroke as

Therapeutic Adjunct (NUVISTA)

NCT number: NCT05390580, Approval Date: 2/4/2025

Study Title: Vagus Nerve Stimulation following a Large Vessel Occlusion Acute Ischemic Stroke

(NUVISTA)

Principal Investigator: [name] MD

Co-investigator(s): [name] [name]; [name] MD

Sponsor or funding source: None

Objectives

To quantify inflammatory markers in the blood of patients who present with ischemic strokes due to large vessel occlusions to Barnes Jewish Hospital, and determine if treatment with auricular transcutaneous vagal nerve stimulation alters the levels of inflammatory markers in these patients over time, and we will explore if it impacts their overall outcome.

Methods and Measures

Design

This is a randomized open-label, with blinded outcome pilot study to evaluate the effect on inflammatory laboratory values and explore clinical outcomes in patients who present with ischemic strokes due to large vessel occlusions and are treated with either current accepted management, or accepted management in addition to transcutaneous auricular vagal nerve stimulation.

Setting

Patients in this study will be inpatient at Barnes Jewish Hospital

Data Collection Criteria

Adult patients who present with acute ischemic strokes due to large vessel occlusions to Barnes Jewish Hospital will be considered for enrollment in this study. Exclusion criteria will include patients <18 years old, patients with presumed chronic large vessel occlusions, posterior circulation LVOs, NIHSS<6, CTP Penumbra <1/3 total ischemic area, pre-morbid modified Rankin score (mRS) >2, unable to initiate treatment under 36 hours from symptom discovery, life expectancy <3 months, patients' undergoing active cancer or immunosuppressive/modulating therapy, or patients with sustained bradycardia on arrival with a heart rate <50 beats per minute.

Sample size

We anticipate enrolling approximately 80 patients into the study, with random assortment to treatment with standard medical care, and standard medical care with transcutaneous auricular vagal nerve stimulation.

Intervention

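### The 90-day mRS is analysed as a change with no stated reference score and no rule for deaths; comparing the attained 90-day mRS would avoid the problem

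*Combined protocol and SAP*

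**What the plan says.** The Expanded Statistical Analysis (rate-of-change section) sets the method: "For 30-day NIHSS changes (vs. baseline) and 90-day mRS changes, we used the parallel model". The parallel model is the linear one used for in-hospital NIHSS. Visit timing is handled by rescaling: "with actual assessment days scaled to standardize the evaluation period to 30 or 90 days, respectively". The model belongs to a family described as follows: "All longitudinal models included treatment, time since LKN, and their interaction term(s) as primary independent variables". It is a mixed model "with person as a random effect, given multiple records per person". The inference is a likelihood ratio test of the treatment-by-time interaction at two-sided 0.05. The adjustment covariates are baseline NIHSS, time to thrombus removal or attempt, and percent reperfusion. No mRS value is among them.

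The documents mention two mRS values before day 90:

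- The pre-morbid score. Data Collection Criteria excludes patients with "pre-morbid modified Rankin score (mRS) >2", so it lies between 0 and 2.
- The day-30 score. Outcome Measure(s) states "we will obtain the mRS data at 30 days over the phone".

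The status of the endpoint is given in Outcome Measure(s): "The secondary exploratory endpoints will be clinical outcomes assessed via the change in daily NIHSS and mRS at 30 and 90 days". Deaths appear in the safety logistic regressions and as part of poor disposition. Nothing says how a death enters the mRS model.

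**The concern.** The mRS describes an attained state, and death is its worst level. Subtracting an earlier score can break that order, because two patients with the same change may have ended in very different states. The reference here is also undefined: the parenthesis that anchors the NIHSS change to baseline is not repeated for the mRS. One candidate reference describes the patient before the stroke; the other is measured after randomisation.

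At stake is the only mRS analysis that the SAP specifies, since the 30-day mRS is collected but given no analysis. As written, an analyst could choose among references and death rules that answer different questions, and a reader could not tell which had been used.

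**Working it through.** The plan gives no figure on this point, so there is none to reproduce.

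**Inputs from the documents:** pre-morbid mRS 0 to 2; mRS at days 30 and 90; linear treatment-by-time model; about 80 patients.
**Assumptions:** death = 6; equal allocation, so 80 / 2 = 40 per arm.

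**1. What the interaction tests.** Suppose each patient has two mRS records, a reference and day 90. The interaction, multiplied by the time between them, equals (mean change in taVNS) − (mean change in sham). Baseline covariates entered as main effects do not alter that contrast when both records are complete. The tested quantity is therefore the difference in mean change.

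**2. Pre-morbid reference.** Change = day-90 mRS − pre-morbid mRS.

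- Deaths: 6 − 0 = +6, 6 − 1 = +5, 6 − 2 = +4.
- Survivors: 3 pre-morbid levels × 6 outcomes = 18 paths, ranging from 0 − 2 = −2 to 5 − 0 = +5.
- Pairs: 3 × 18 = 54.
- Death ranks better in 1 pair: 2→6 (+4) against 0→5 (+5).
- Death ranks equal in 3 pairs: 2→6 and 0→4 (both +4); 2→6 and 1→5 (both +4); 1→6 and 0→5 (both +5).
- Death ranks worse in the other 54 − 4 = 50.

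These are counts of possible pairs, not patient frequencies.

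Expected arm difference in change = (difference in mean day-90 mRS) − (difference in mean pre-morbid mRS). The pre-morbid score precedes randomisation, so the second term is 0 in expectation and the comparison is unbiased.

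**3. Day-30 reference.** Change = day-90 mRS − day-30 mRS.

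- Death by day 30: 6 − 6 = 0.
- Survivors: 6 × 6 = 36 paths, of which 15 worsen, 6 are stable and 15 improve.
- The early death ranks better than 15 paths, equal to 6 and worse than 15.
- A between-arm difference already present at day 30 goes into the treatment main effect, which the stated test does not examine.

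**4. Deaths without an mRS record.** No misranking arises. But the day-90 data then come from survivors only, with deaths handled as missing.

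**5. Illustrative size.** Both simulations use 40 per arm, unadjusted t-tests and assumed distributions.

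First simulation, 4,000 trials:

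- Day-90 mRS 0 to 6 in sham: 6, 10, 13, 16, 20, 13, 22%.
- Day-90 mRS 0 to 6 in taVNS: 8, 13, 15, 17, 19, 11, 17%.
- Pre-morbid 0/1/2: 65/20/15%. Survivors end no better than their pre-morbid level.
- 75% of deaths have occurred by day 30; the remaining deaths are at mRS 5 on that day.
- 35% of survivors are one grade worse at day 30 than at day 90, capped at 5.

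| Analysed quantity | Mean arm difference | SD of the difference | Power |
|---|---|---|---|
| Attained 90-day mRS | −0.32 | 0.40 | 12.6% |
| Change from pre-morbid | −0.32 | 0.42 | 11.3% |
| Change from day 30 | −0.03 | 0.11 | 6.2% |

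Second simulation, 3,000 trials per effect size, with a latent logistic mRS and pre-morbid 0/1/2 in 60/25/15%. The effect is complete by day 30 and maintained, with true differences of −0.8 and −1.2:

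- Attained mRS: power 48% and 81%.
- Change from pre-morbid: 46% and 80%.
- Change from day 30: 5% and 6%, mean difference −0.03.

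**The case against.** The strongest reply is that the text points to a change anchored at baseline. The mRS clause runs parallel to an NIHSS change taken against baseline, time is counted from last known normal, and the evaluation period is standardised to 90 days. A change from day 30 to day 90 would span 90 − 30 = 60 days. Under the baseline reading a change score is a valid randomised comparison, and the figures above show almost no loss. The simulations place most or all of the effect before day 30, so a day-30 change must come out near zero, and they use t-tests rather than the planned adjusted mixed model. The records review could also supply an admission mRS, although none is scheduled. Finally, excess mortality would show in the safety regressions and in poor disposition.

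Most of this stands, and it limits the point. A reader might infer that deaths are scored as equal to or better than survival. The documents do not say so, because they give neither the reference nor a code for death. A reader might also infer that the pre-morbid score cannot serve as a reference; for comparing arms it can. Nor does a pre-morbid-2 death undercount its arm by 2 / 40 = 0.05: the same 2 points are subtracted whether that patient lives or dies, and in either arm, so only chance imbalance remains.

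What the reply does not remove is the silence on reference and deaths, or the fact that each reading available from the scheduled data has a defect.

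**Conclusion.** The point holds in a conditional form. The plan defines neither the reference for the 90-day mRS change nor the handling of deaths, and it schedules no mRS after the stroke and before treatment. With death = 6, the pre-morbid reference misorders 4 of 54 possible pairs but leaves the arm comparison unbiased at a small cost in power (46% and 80% against 48% and 81%). The day-30 reference gives early deaths a change of 0 and removes effects already present by then. Without an mRS for deaths, the day-90 data cover survivors only.

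It would go too far to conclude that the trial's functional result is lost. The near-total loss of power needs both the less natural reference and an early, sustained effect, and every power figure rests on assumed distributions. The endpoint is secondary and exploratory in a pilot study, so the primary biomarker conclusions are untouched. The change should still be made, because one inexpensive analysis avoids all three defects.

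**What to change.** Replace the analysis of 90-day mRS changes with wording such as:

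> The mRS attained at 90 days (0 to 6, with death at any time up to the assessment scored as 6, the worst level) will be compared between arms by proportional-odds regression, adjusted for pre-morbid mRS, baseline NIHSS, time from LKN to thrombus removal or attempt, and percent reperfusion. The 30-day mRS will be analysed in the same way. No mRS change or slope will be computed.

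This leaves 0 pairs in which a death ranks equal to or better than survival, keeps any effect already present at day 30, and includes deaths. If the mixed model is kept as a supplementary analysis, state which mRS records enter it, how deaths are coded and what assessment day a death receives.

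The cost is SAP wording and, since the section is written in the past tense, possibly a re-run; in that case, report when the change was made. The 30- and 90-day mRS are already scheduled, and the pre-morbid score is needed for eligibility. The small downside is that the result is a common odds ratio resting on proportional odds, not points of change.

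### If the 30-day NIHSS model has two records per patient, entering baseline NIHSS as an outcome record does not adjust for it; adjusting would add between about 0 and 18 points of power

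*Combined protocol and SAP*

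**What the plan says.** All of the modelling text is in the Expanded Statistical Analysis, under the heading on rate of change in cytokines, WBC and neurological outcomes.

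- **Fixed effects:** "All longitudinal models included treatment, time since LKN, and their interaction term(s) as primary independent variables". The treatment main effect is free, so the arms may differ at baseline.
- **Random effect:** the models are fitted "with person as a random effect, given multiple records per person".
- **Endpoint:** "For 30-day NIHSS changes (vs. baseline) and 90-day mRS changes, we used the parallel model". The follow-up score is then put on a common time axis, the SAP says, "with actual assessment days scaled to standardize the evaluation period to 30 or 90 days, respectively".
- **Test:** "Treatment-time interactions were tested using likelihood ratio tests comparing models with and without interaction term (NIHSS, mRS" and, for cytokines and WBC, several terms), "with significance at two-sided α =0.05".
- **Covariates:** adjustment is for baseline variables, "including baseline NIHSS (except in NIHSS models, which included this observation"). The other two are time from LKN to thrombus removal or recanalization attempt, and "percent reperfusion (0-100%) based on TICI score to obtain a single semicontinuous measure".

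The SAP does not state how many records per patient enter the 30-day NIHSS model. Neither the protocol nor the SAP gives an SD, a baseline-to-30-day correlation, an effect size or a power figure for NIHSS. The protocol's Outcome Measure(s) section makes clinical outcomes secondary and exploratory.

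**The concern.** The SAP's reason for dropping baseline NIHSS is that the baseline score is already in the model. Being in the model as an outcome is not the same as being adjusted for. With a free treatment main effect, any baseline difference between arms is absorbed by that term, and the interaction measures only the difference in change. In effect the coefficient of baseline is fixed at 1 instead of being estimated.

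Two things are at stake. One is precision on a clinical endpoint tested formally in about 80 patients. The other is that part of any chance imbalance in baseline severity can carry into the estimate from this one trial.

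**Working it through.** The plan has no figure of its own to reproduce, so the check is of structure first and then of size over a range.

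**Inputs.** N is about 80 (protocol, Sample size). I assume 40 per arm, because no allocation ratio is given. Two-sided alpha is 0.05 (SAP). The correlation rho and the SDs s0 (baseline) and s1 (30 days) are not given. I take rho = 0.3, 0.5, 0.7 and k = s1/s0 = 0.8, 1, 1.25, 1.5. Patients with NIHSS below 6 are excluded (protocol, Data Collection Criteria), which truncates baseline but not follow-up, so k above 1 is plausible.

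**Step 1: what the interaction estimates.** With two records, time 0 and time 1 (one unit = 30 days):

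y = b0 + b1·arm + b2·time + b3·arm·time + covariates + person effect + error.

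Subtracting a patient's two records gives: change = b2 + b3·arm + error difference. The person effect, b1 and the baseline covariates all cancel. With complete pairs, b3 is therefore the difference between arms in mean change.

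Fitting this model to simulated trials of 80 confirmed it. In one trial the interaction was −0.6466 and the difference in mean change −0.6466, with likelihood ratio p = 0.0025 and change-score t-test p = 0.0029. Removing a retained baseline covariate left the interaction unchanged. Letting start times vary between patients moved it only slightly (for example −0.326 against −0.324).

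**Step 2: variances.**

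- Change score: s0² + s1² − 2·rho·s0·s1
- Adjusted for baseline (ANCOVA): s1²(1 − rho²)
- Difference: s0² − 2·rho·s0·s1 + rho²·s1² = (s0 − rho·s1)², which is never negative and is zero only when rho·s1 = s0.

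Variance ratio: VR = (1 + k² − 2·rho·k) / [k²(1 − rho²)].

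**Step 3: power.** An effect with 80% power under the change score has a standardized value of 2.8016. After adjustment, power = Φ(2.8016·√VR − 1.96). At rho = 0.5 and k = 1: VR = 1/0.75 = 1.33, and 2.8016 × 1.1547 − 1.96 = 1.275, giving 89.9%.

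Power after adjustment, where the change score has 80% (VR in brackets):

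| 30-day SD / baseline SD | rho 0.3 | rho 0.5 | rho 0.7 |
|---|---|---|---|
| 0.8 | 98% (1.99) | 96% (1.75) | 94% (1.59) |
| 1.0 | 94% (1.54) | 90% (1.33) | 86% (1.18) |
| 1.25 | 89% (1.27) | 84% (1.12) | 81% (1.02) |
| 1.5 | 85% (1.15) | 81% (1.04) | 80% (1.00) |

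**Step 4: simulation.** With 40 per arm, 6,000 trials per setting, and the effect set so that ANCOVA has a nominal 80%, power for change score against ANCOVA was 67.3% against 78.7% (rho 0.5, k = 1) and 72.5% against 78.7% (rho 0.7, k = 1). At rho 0.6 and k = 1.5 it was 80.0% against 79.8%, so no gain there.

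**Step 5: chance imbalance.** Each NIHSS point of baseline imbalance leaves (1 − rho·k) points in the change-score difference. With equal SDs that is 0.7, 0.5 and 0.3 points at rho 0.3, 0.5 and 0.7. At rho = 0.7 and k = 1.5 it is 1 − 1.05 = −0.05, essentially nothing.

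**The case against.** **The two-record structure is not stated.** The 30-day analysis is described as parallel to the in-hospital NIHSS model, which uses repeated scores. If in-hospital scores enter too, the test compares slopes, and neither the identity in Step 1 nor the table applies. This stands as a condition on the whole point. Two records remains the natural reading, because the endpoint is a change from baseline, time is rescaled to one 30-day period, and in-hospital NIHSS is described separately.

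**The size is unknown.** A reader might infer a fixed loss of about 10 points. The documents do not support that: it is the case of equal SDs and rho near 0.5, and the gain is negligible if 30-day NIHSS is sufficiently more variable than baseline. A reader might also infer that a change score always over-corrects for baseline. It does so only while rho·s1 is below s0. Both limits stand.

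**The test is valid and the endpoint exploratory.** Under randomization the change-score estimate is unbiased, and there is no power target to miss. This stands too, and it makes the point an improvement in efficiency.

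**Changing now could be data-driven.** The SAP is written in the past tense, and some choices refer to plots of the data or to the number of observations available. This is a fair caution, and the fix allows for it.

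**Conclusion.** On the two-record reading, the 30-day NIHSS test is a change-score comparison in which baseline NIHSS is not adjusted for, and the two retained covariates, as main effects, do not change the estimate. The direction of the loss needs no assumption about rho or the SDs: apart from one degree of freedom, adjusting for baseline cannot do worse. The size does need them. Over the ranges shown, with 40 per arm assumed and complete pairs, the gain runs from about 0 to 18 points on a base of 80%.

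It would be wrong to infer that the planned test is biased or has an inflated type I error. This is a specific, near-free gain in precision on an exploratory endpoint, in line with the SAP's own use of baseline NIHSS as a covariate in its other longitudinal models.

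**What to change.** 1. State which records enter the 30-day NIHSS model.
2. Adjust the 30-day score for baseline NIHSS in one of two ways: ANCOVA of the follow-up score on treatment, baseline NIHSS and the two other a priori covariates; or a mixed model with baseline means constrained equal across arms, which stays within the SAP's framework.
3. Report the adjusted arm difference with its 95% confidence interval, and keep the change-score test as a sensitivity analysis. If outcome data have already been seen, report both and label the adjusted analysis accordingly.
4. Reconcile the assessment schedule. The protocol's Outcome Measure(s) section plans mRS by phone at 30 days, and NIHSS with mRS at a 90-day visit. The SAP analyses NIHSS at 30 days and mRS at 90 days. No 30-day NIHSS is explicitly scheduled, so its availability has to be settled first.

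The cost is a few lines of SAP text and one further model on data already planned, with no new data collected. ANCOVA makes no direct use of patients without a follow-up score, but they contribute almost nothing to the two-record interaction either.
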